### **Health and Service Use and Productivity level**

The net costs and benefits of the intervention compared to the control will be described and reported in accordance with the Consolidated Health Economic Evaluation Reporting Guidelines (CHEERS).[84] For each intervention arm, the probability of resource use and associated costs will be reported. Cost estimates will be presented in terms of direct costs (e.g. healthcare), indirect costs (e.g. lost productivity) and out-of-pocket costs. Unit prices for resources utilised will be sourced from the most appropriate and up-to-date source (PHARMAC). Costs will be measured in real prices for the reference year (e.g. 2023). Where prices in 2023 are unavailable, adjustment to the real price will be made using the published health sector specific deflator/inflators.

## RANDOMISATION

Randomisation will be conducted in REDCap. On completion of the baseline assessment, the study manager will randomise participants into HWC (n=180) or UC (n=180). Stratified minimisation randomisation will be used to balance prognostic factors: age (<55, ≥55 years, sex (Male, Female), ethnicity (European, Pacific, Māori, Asian and MELAA (Middle Eastern, Latin American and African)).

### Randomisation Procedure

The randomisation form in REDCap will be a hidden form, visible only to the study managers and data manager. The research assistants will not have access to the randomisation form. The randomisation parameters will be predefined, the stratified randomisation module will be selected, and the strata will be selected as: age (<55, ≥55 years), sex (M, F); and four ethnicity categories (1) European, (2) Pacific, (3) Māori, (4) Asian and MELAA (Middle Eastern, Latin American and African). The Dashboard display will show the allocation as HWC or Usual Care.

## PROCESS FOR PHYSICAL MEASUREMENTS

### 21. STUDY EQUIPMENT:

- Cardiocheck blood test kit
- Omron Blood pressure monitor
- Stadiometer
- Weight scales
- Gloves
- Medical Masks
- Hand sanitizers and wipes
- Biohazard waste bins

Participants will be requested to come in light clothing and will be asked to remove their shoes for height and weight measurement. Measures will include, in this order, BP measured after 10 minutes of rest using a Omron digital blood pressure monitor and European Society for Cardiology guidelines,[85] height with a stadiometer, weight with Omron digital scale, a capillary blood sample using a single use lancet and capillary tube will be used with a Cardiochek point of care monitor to

obtain non-fasting glucose, total, HDL and LDL cholesterol and triglyceride levels. Assessments should take 30 minutes.

People identified as having high risk levels of BP will be encouraged to seek medical attention for further management. Please refer to the Blood Pressure Assessment section in Appendix A for further information (systolic BP reading over 220 mmHg or diastolic BP reading over 140 mmHg requires immediate medical attention: systolic reading over 180 or diastolic reading over 110 require the participant to seek medical advice in the next 48 hours).

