## 18. ASSESSMENTS

There will be a total of five assessments: baseline, 3, 6, 9 and 12 months. Eligible participants will be contacted by CRAs to book appointments for assessments. The baseline and 6-month assessments will be conducted face to face to allow the measurement of the primary outcome metrics for the LS7 (height, weight, blood pressure, blood glucose and blood cholesterol) as well as cognitive assessments. The 3-, 9- and 12-months assessments will be conducted over telephone, at a suitable time.

For face-to-face assessments, the participant will have the option of attending a clinic at one of the three locations at the AUT campuses (AUT North, City or South). Participants travelling to clinics will be provided a petrol or supermarket voucher (NZ \$20) for parking or travel costs.

Participants who are unable to travel to clinic sites will be offered a home visit to conduct the baseline and 6-month assessments.

---

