## 31. SECONDARY END POINTS

Secondary outcomes include: (1) difference in the mean change in the LS7 scale score at 6 months post-randomisation between UC and HWC (2) the change in individual lifestyle components of the LS7 scale (BMI, smoking, physical activity, and diet) at 6 and 12 months; (3) diastolic BP (mmHg); (4) quality of life (EQ-5D-5L), (5) awareness of stroke risk factors and warning signs, (6) medication adherence (7) cognitive outcomes (8) adverse events including hospitalisations; and (9) health service use and costs.

The LS7 scale includes BP, cholesterol, blood glucose, BMI, smoking, physical activity, and diet. The score of LS7 will be calculated by providing 2 points for ideal, 1 point for intermediate, and 0

points for poor status of each of the 7 individual factors. Ideal levels of health factors were: non-smoker or quit >1 year ago; BMI <25 kg/m^2; BP <120/80 mm Hg; total cholesterol <200 mg/dL; fasting blood glucose <100 mg/dL; ≥150 min/week of physical activity; and a healthy diet score (≥4 components). Study participants who were treated to target levels for hypercholesterolemia, hypertension, or diabetes mellitus were classified as intermediate for the respective health factor. Thus, the LS7 summary score will range from 0 to a maximum of 14 points, with a higher score indicating healthier status.

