### Measurement of Height

Seca model 214 stadiometer, with a maximum 2 metre range, will be supplied for height measurement.

Assemble the stadiometer by placing the baseplate on the floor, selecting as firm a level as possible. Insert the measuring stick components into the baseplate.

[figure not shown]
Ask the participant to remove their shoes and stand on the base plate with their back to the measuring stick. The participant should be told to stand as tall and straight as possible with feet on the “feet outline” of the baseplate and arms held loosely at the side and shoulders relaxed. Heels, buttocks and shoulders should be against the measuring stick.

Ask the participant to breathe in and look straight ahead.

Read the height to the nearest cm. Make one measurement of height. Record the value on the PRF.

Record to nearest cm (round 0.1- 0.4 downwards and 0.5 - 0.9 upwards to the nearest whole number).

*NB: If the participant is unable to stand, estimate the height by asking the participant.*

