### *Measurement of Weight*

Salter bathroom scales model 9175

with a maximum 200kg range, will be supplied for weight measurement as required in relevant section of REDCap 'baseline assessments – physical measurements'. The scales have been calibrated and will be recalibrated annually.

All weight measurements are to be in kilograms. Ensure that the weight mode switch on the underside of the scales is set to KG.

Weigh the participant without their shoes. The participant should ideally *wear light indoor clothing* only. Remove any heavy items of clothing, heavy items from pockets, and heavy jewellery.

Place the scales on a flat level surface.

Press the centre of the scale platform firmly with your foot to activate the scales.

Remove foot and wait for the display to show a '0.0' reading.

When zero is displayed ask the participant to step onto the scales and stand still.

The participant should stand on the centre of the scales without support. Weight should be evenly distributed on both feet and the participant should look straight ahead.

Make one measurement of weight – the weight display will appear after 2-3 seconds.

Record weight to nearest 0.1kg.

Warning indicators are: Err = overload (maximum load is 200kg) and picture of a battery = replace batteries.

Batteries: when necessary replace with 4 new AA size batteries. Ensure +/- terminals are the correct way round.

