**Part D: BMI**

15D.1. Height (cms)

\_\_\_\_\_

15D.2. Weight (kgs)

\_\_\_\_\_

15C.3. BMI (Formula: Calculated BMI  
weight(kg)/height(m^2))

\_\_\_\_\_

15C.4. BMI LS7 Score (Formula: BMI < 25kg/m^2 LS7 score  
= 2, BMI 25-29.99 kg/m^2 LS7 score = 1, BMI 30+ kg/m^2  
LS7 score = 0)

\_\_\_\_\_

**Part E: Smoking**15E.1. Which of this best describes your current  
smoking status?

- Current smoker  
 Ex-smoker, quit smoking within the last 12 months  
 Never smoked, or last smoked more than 12 months  
 ago (cigarettes, ready-made or roll your own;  
 cigars cigarillos or pipe)

15E.2. If current smoker, average number of cigarettes  
smoked per day?

\_\_\_\_\_

15E.3. LS7 Smoking score

\_\_\_\_\_

**Part F: Recreational Drugs: Additional Section (Not a part of LS7 scoring)**15F.1. Smoked any of the following products in the  
past year.

- Tobacco Vapes  
 Hookah/Shisha Cannabis  
 Other recreational drugs

15F.2. If consumed recreational drugs, please  
specify.

\_\_\_\_\_

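### Re-reading height at 6 months adds small, avoidable noise to BMI change and the LS7 BMI item; separately, the protocol names two different weighing scales

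*Protocol*

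**What the plan says.** **Height.** Section 18 states: "The baseline and 6-month assessments will be conducted face to face to allow the measurement of the primary outcome metrics for the LS7". The bracket that follows includes height, so height is planned at both visits. Appendix A (Measurement of Height) asks for one reading and instructs: "Record to nearest cm (round 0.1- 0.4 downwards and 0.5 - 0.9 upwards to the nearest whole number". A participant who cannot stand is asked for their height. The follow-up form (Appendix C, Form F, Section 15 Part D) repeats the field "15D.1. Height (cms" and gives a BMI and an LS7 BMI score from weight and height on that form, with cut-offs at 25 and 30 kg/m². Nothing in the protocol says that the baseline height is reused.

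**Weight.** Section 21 specifies "height with a stadiometer, weight with Omron digital scale". Appendix A (Measurement of Weight) specifies "Salter bathroom scales model 9175" and adds "Record weight to nearest 0.1kg" and "The scales have been calibrated and will be recalibrated annually".

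**Use.** Section 31 lists as a secondary outcome "the change in individual lifestyle components of the LS7 scale (BMI, smoking, physical activity, and diet) at 6 and 12 months". BMI is also one of the seven items, scored 0, 1 or 2, of the LS7 total. The 12-month contact is by telephone, so the check below concerns the 6-month change.

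**The concern.** A change in BMI over 6 months should reflect a change in weight. If each visit's BMI uses that visit's own height reading, any disagreement between the two readings appears as a BMI change that did not happen. Height enters BMI squared, and the recorded heights move in whole centimetres, while weight is recorded to 0.1 kg. Near 25 or 30 kg/m² a small disagreement also becomes a full LS7 point.

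At stake is some precision on one secondary endpoint and on one of seven LS7 items. With one height used at both visits, BMI change is the weight change divided by a fixed height squared. An error in that height then only rescales the weight change slightly.

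The two scale names are a separate matter. An assessor cannot follow both sections as written.

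**Working it through.** **The plan's own figure.** There is none to reproduce. The protocol states no BMI effect, SD or power, and its sample size of 360 rests on systolic blood pressure.

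**Inputs from the protocol.** Height is read once to a whole centimetre and weight to 0.1 kg (Appendix A). The BMI cut-offs are 25 and 30 (Form F). With 20% of 360 lost (section 7), 288 remain, or 144 per arm.

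**Assumed inputs, not in the protocol.** Mean height 170 cm (SD 9.5); mean BMI 29 (SD 5); SD of true BMI change 1.0 to 2.0 kg/m²; single-reading height error SD 0 to 0.8 cm.

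**Step 1: effect of 1 cm.** At 170 cm and BMI 30, weight is 30 × 1.70² = 86.7 kg. With a second height of 169 cm, BMI is 86.7 / 1.69² = 30.36, a false change of 0.36 kg/m². One kilogram of weight moves BMI by 1 / 1.70² = 0.35, and 0.1 kg by 0.035. A 1 cm disagreement therefore counts for about as much as 1 kg, ten times the resolution of the weight record.

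**Step 2: added SD by formula.** If each reading has error SD e plus rounding to 1 cm (variance 1/12), the SD of the difference between two readings is √[2(e² + 1/12)] cm. Per centimetre, BMI moves by about 2 × 29 / 170 = 0.341 kg/m².

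- e = 0.3: √[2(0.09 + 0.083)] = 0.589 cm; × 0.341 = 0.20 kg/m²
- e = 0.5: √[2(0.25 + 0.083)] = 0.816 cm; × 0.341 = 0.28 kg/m²
- e = 0.8: √[2(0.64 + 0.083)] = 1.203 cm; × 0.341 = 0.41 kg/m²

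The formula treats the two rounding errors as independent. It does not apply at e = 0, where both visits round to the same value and the error cancels.

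**Step 3: simulation.** 500,000 simulated participants, with height rounded at both visits, comparing BMI from two heights with BMI from one carried-forward height:

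| Reading-error SD (cm) | Recorded heights differ | Added SD of BMI change (kg/m²) | Rise in variance at true-change SD 2.0 / 1.5 / 1.0 | LS7 BMI category differs |
|---|---|---|---|---|
| 0 | 0% | 0 | 0 | 0 |
| 0.3 | 34% | 0.20 | 1.0% / 1.8% / 4.2% | about 1.5% |
| 0.5 | 51% | 0.29 | 2.0% / 3.7% / 8.0% | about 2.5% |
| 0.8 | 67% | 0.42 | 4.3% / 8.0% / 17.5% | about 4% |

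Of 288 participants, 1.5 to 4% is about 4 to 12 people.

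**Step 4: power for BMI change.** Take a difference that 144 per arm would detect with 80% power, true-change SD s and added SD a. Power becomes Φ[2.80 / √(1 + a²/s²) − 1.96]. For a = 0.25 it is 77.6% (s = 1.0) to 79.4% (s = 2.0). For a = 0.42, the worst row of the table, it is about 73% to 78%.

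**Step 5: LS7 total.** With no true change, the false item changes have SD 0.124, 0.160 and 0.201, so variances of 0.015, 0.026 and 0.040. Section 6 gives an LS7 score SD of about 2.0, a variance of about 4. The false changes amount to 0.4 to 1.0% of that. The protocol gives no SD for LS7 change, so this is only a rough scale.

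**The scales.** The equipment list in section 21 says only weight scales, the text beneath it says Omron, and Appendix A says Salter 9175. No section assigns one make to one visit or site, or requires the same make at both visits. No calculation is possible from that.

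**The case against.** The case for leaving the plan alone has several parts.

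- **The printed form is weak evidence of procedure.** Form F serves all four follow-ups, including telephone calls at which height cannot be measured, and it still carries baseline eligibility text. Its comorbidity question hides items already ticked, so the database can use earlier entries, and a printed form cannot show a pre-filled field. This stands in part: that BMI uses a new height is the natural reading, not an explicit rule. But section 18 plans height at 6 months, and nothing says otherwise.
- **A second reading can expose a mis-entered baseline height.** True, and reusing the baseline height would carry an undetected error forward. A plausibility check at entry meets most of this.
- **The sizes rest on assumptions.** They do, and the 18% end needs both the largest reading error and the smallest true-change SD.

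A reader might also infer more than the protocol supports:

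- *That whole-centimetre rounding is the cause.* Rounding a perfectly repeated height cancels. The noise comes from the second reading, and rounding only coarsens it.
- *That self-reported height is a material problem.* Participants are expected to be independent (mRS 0 to 2) or to have mild deficits, and rest-home residents are excluded. Inability to stand should be rare.
- *That baseline and 6-month weights come from different makes.* The two names conflict, but no section shows that a participant would change device. Appendix A also describes one calibrated model.
- *That the comparison is biased or the primary result affected.* Assessors are to be blinded and both arms follow one procedure. Section 18 speaks of primary outcome metrics, but section 30 defines the primary endpoint as systolic blood pressure.

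**Conclusion.** The point holds as a minor matter of precision. As written, the protocol takes height again at 6 months, calculates BMI on the follow-up form and does not carry the baseline height forward. Under the stated assumptions this adds an SD of about 0.2 to 0.4 kg/m² to BMI change and raises its variance by about 1 to 18%, with 2 to 8% at a 0.5 cm reading error. About 1.5 to 4% of participants would be placed in a different LS7 BMI category. The effect on the LS7 total is very small. The error should not differ by arm, and the primary endpoint and the sample size of 360 are unaffected.

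The conflict between the Omron and Salter scales is certain as a matter of text. Whether it affects any weight change is not settled by the protocol, so it is a consistency correction only.

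**What to change.** 1. State that BMI at every visit is calculated from the one baseline height, and pre-fill item 15D.1 on Form F from Form B. If the database already does this, one sentence in the protocol is enough.
2. Add a plausibility check on the baseline height when it is entered, because an undetected error there would carry forward.
3. Name one scale make and model in both section 21 and Appendix A, and use the same model for a participant at baseline and 6 months.

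The cost is one pre-filled field, one range check and one corrected equipment line. The 6-month visit loses a measurement. Eligibility, intervention and sample size do not change.

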## THE HEALTH AND WELLNESS COACHING INTERVENTION

---

### 22. TRAINING THE COACHES

Research staff will attend an intensive 4-week coaching course, at Momentum Coaching ([www.coachmomentum.co.nz](http://www.coachmomentum.co.nz)), with two sessions in the first two weeks and 4 which includes training in core coaching competencies and code of ethics, developed by the International Coach Federation (ICF) to support greater understanding of the skills and approaches used in the coaching profession. ICF coaching is an internationally recognized approach effectively used in various settings,[86] including our previously accomplished primary stroke prevention trial.[87] Coaches will receive regular group supervision, facilitated by a registered ICF coach, using a small group approach.[87] This model increases the capacity of the team to think from multiple perspectives, translating diverse experiences and issues to the group.

---

### 23. TRAINING MATERIALS

The coaches will be provided with relevant materials during training. The training is outlined as below:

#### **Day 1:**

1. Establish group rapport, practicalities e.g. Paperwork and safety procedures. Each person introduces themselves, share their interest in the project.
2. Develop the group contract
3. a. Define Life Coaching, increase understanding of differences between Coaching, Counselling, Psychotherapy, Mentoring and Consulting
4. Recognise coaching attributes
5. Explain and discuss the elements of the Co-Active, give group feedback.
6. a. Identify and be able understand the 3 levels of listening. Practice new listening skills.

7. a. Explain and demonstrate the Circle of Life tool, practise coaching in pairs, in whole group acknowledge each coach for the competencies done well in coaching practice, each person identify one competency that could be done better.

### **Day 2:**

1. Demonstrate coaching by listening and responding in a coach-like manner in response to group members' sharing of breakthroughs and challenges of the week. Participate in group discussions, giving and receiving feedback. Engage in clearing personal issues that could otherwise prohibit full participation in session.
2. Discuss the importance of the Core Competencies and how we use them as the Foundation in coaching.
3. Recognise and identify various types of coaching questions, define specific types of questions and explain the effect of various questions types, differentiate effective and ineffective question types.
4. Explain, discuss and demonstrate Coaching Skills such as: paraphrasing, reframing, clarifying, analogy and metaphor, distinctions, bottom-lining, intruding, metaview, championing and challenging.
5. Practise coaching in pairs. In whole group acknowledge each coach for the competencies done well in coaching practice. Each person identify one competency that could be done better.

### **Day 3:**

1. Define Personal Values. Understand the importance of Values in a coaching forum in order to facilitate learning and results from a deep understanding of self. Practise coaching in pairs using Personal Values Card Sort. Acknowledge each other for competencies demonstrated and name where improvement is possible.
2. Introduce a variety of Assessment tools and discuss the benefits of each. Discuss how to interpret the information attained and how to create a coaching plan most relevant to each specific clients' needs.
3. Name and demonstrate examples of the SMARTPP GOALS components. Establish a variety of goal-setting tools for use in coaching sessions. Become practiced at utilising a variety of methods/tools for goal- setting.

### **Day 4:**

1. Experience the psycho-geometric profiling exercise (Susan Dellinger PhD). Identify and recognise own preferences in relation to psycho-geometric profiling, apply this tool in coaching session, gain awareness of uses of this tool in coaching sessions.
2. Demonstrate the use of the Focus Framework as a goal-setting Strategy, Remediation resource for under-achievement or Time-management resource.
3. Introduce the Decisional Balance framework as a resource for ambivalence or indecision. Practise coaching each other, give feedback on coaching.

### **Day 5:**

1. Gain knowledge and understanding of the MOMENTUM Model of Coaching. Explain how it aligns with the Core Competencies.
2. Introduce the Coaching Evaluation Form. Discuss the use of it in conjunction to ongoing supervision.
3. Discuss the importance of identifying beliefs in coaching in the context of how they can help or hinder achievement. Introduce brainstorming as a useful resource in uncovering hidden beliefs.
4. Extend the topic of Beliefs into the concept of Self-Talk, The Inner Critic / Ally. Demonstrate the use of the resources. In pairs, practice coaching using the Self-Talk concept. Group feedback.
5. Understand the powerful impact of 'metaview' coaching by identifying and coaching PATTERNS (instead of separate scenarios). Demonstrate the process by using the Recurring Pattern Intervention concept, using one of the trainees' personal examples. Group feedback.
6. Coaching practice in 3's. Coach, coachee, observer.

### **Day 6:**

1. Brainstorm all coaching knowledge covered on the course to-date. (Including the 8 Main Competencies)
2. Introduce the Relationship Overview resource. Recap Momentum Model.
3. Coaches practise coaching in 3's, feedback as a group. Practise filling out Coaching Evaluation Form
4. Introduce the Time Management resources: DDDS, Ideal Weekly Planner, Daily Prioritising, Weekly Prioritising, Weekly Planner with roll-over.
5. Discuss and agree upon Consistency of Coaching Structures and Toolkit for measurement, Supervision Structure.

---

## 24. OUTLINE OF SESSIONS

Topic	Aims/Strategies for the first session (in-person)
Session opening	Introductions, setting expectations, discussing the study and confidentiality, setting agenda
Health risk assessment	Focus on positive and strengths, values and readiness to change for participant, make appropriate referrals
Wellness vision	Dreams and vision of self and wellbeing in 3-5 years, identify values and motivators
Three month goals	Mid-term goals for consistent behaviours to be doing in three months' time, consider barriers and supports
Weekly goal(s)	First experiment and short-term step forward in an area that the participant is motivated and ready to change
Session close	Affirm belief in the participant and their autonomy, review how the process can be improved, schedule next session
Topic	Aims/Strategies for the first session (over the telephone or in-person, if required)

Session opening	Check in, highlight of the week, set the agenda
Review weekly goals	Focus on positive, explore full experience, reflect participant's strengths and values. Review vision and three month goals. Confirm the vision and three month goals are still where the client is heading, only done once per month
General moment	Participant identifies a target behaviour to address, explore ideal situation, best past experience, values and strengths, and brainstorm ideas
Set weekly goals	Next step in behaviour change in an area the participant is motivated and ready to change, SMART (Specific, Measurable, Action-based, Realistic and Time-bound) goals
Session close	Affirm belief in the participant and their autonomy, review how the process can be improved, schedule next session (if relevant)

Data from the ARCOS V study on stroke risk factor prevalence and significance by age, sex and ethnicity, life satisfaction and other measures will guide the emphasis of the intervention on which particular health behaviours to focus on. As such, providing/referring to educational material is relevant to this model, including information booklets from the Heart and Stroke Foundation (<https://www.heartfoundation.org.nz/resources>) which include recommendations and guidelines on duration and frequency of exercise, weight loss, healthy eating, smoking cessation, and reducing alcohol intake,[88] and information about the free Stroke Riskometer mobile app (for stroke awareness and risk assessment, <https://nisan.aut.ac.nz/Stroke-Riskometer>). This is also in line with recent evidence recommending that RCT's for secondary disease prevention in TIA/minor stroke should include a combination of educational and behavioural interventions.[89-91]

---

